8 STUDY ASSESSMENTS AND PROCEDURES

8.1 ENDPOINT AND OTHER NON-SAFETY ASSESSMENTS

Demographics: Demographic information will be collected, including: gender, age, race, ethnicity, language, height, weight, marital status, employment status, date of MG diagnosis, and e-mail address for study contact).

Medication Review: At study enrollment, participants' prescription medications will be recorded and tracked for the study duration. Medication data will be used for exploratory purposes.

Treatment Adherence: The participant's treatment adherence will be measured to determine tolerability of acupuncture. We will record the number of attended acupuncture sessions. We will also record participants' ability to maintain the acupuncture duration of 30 minutes per session.

Symptom Severity Scale: This scale will assess the participant's usual symptoms of MG and the severity of their symptoms. This scale was custom designed for this study.

Quality of Life: Participants will be asked to complete the MG-QOL15,¹⁴ a brief 15-item disease specific questionnaire that is designed to assess aspects of quality of life in Myasthenia Gravis. It includes questions regarding quality of life, such as vision, speaking, eating, and activities.

Activities of Daily Living: Participants will be asked to complete the MG-ADL,¹⁵ an eight-item patient-reported scale developed to assess MG symptoms and their effects on daily activities. It combines 2 items on daily life activities (ability to brush teeth or comb hair and ability to arise from a chair) with 6 MG symptoms: diplopia, ptosis, chewing, swallowing, voice/speech problems, and respiratory symptoms.

A strong positive correlation between the MG-ADL and the MG-QOL15 ($r = 0.76$, $P < 0.0001$) has been previously demonstrated.¹⁵

Qualitative Feedback Survey: A list of qualitative feedback survey questions will allow for participant's to discuss their experience with acupuncture treatment.

8.2 SAFETY ASSESSMENTS

Assessment of Adverse and Serious Adverse Events:

AEs and SAEs will be monitored by acupuncturists during acupuncture treatment sessions, and by study staff. The acupuncturists and research staff will immediately notify the Principal Investigator and utilize the eCRF to record any AEs or SAEs. The PI and the study physician will review and categorize all AEs or SAEs and report them accordingly, as discussed below.

8.3 ADVERSE EVENTS AND SERIOUS ADVERSE EVENTS

8.3.1 DEFINITION OF ADVERSE EVENTS

This protocol uses the definition of AE from 21 CFR 312.32 (a): any untoward medical occurrence associated with the use of an intervention in humans, whether or not considered intervention-related.

8.3.2 DEFINITION OF SERIOUS ADVERSE EVENTS

This protocol uses the definition of SAE from 21 CFR 312.32 (a): An AE or suspected adverse reaction is considered "serious" if, in the view of either the investigator or study clinician, it results in any of the following outcomes: Death, a life-threatening AE, inpatient hospitalization or prolongation of existing hospitalization, a persistent or significant incapacity or substantial disruption of the ability to conduct normal life functions, or a congenital anomaly/birth defect. Important medical events that may not result in death, be life-threatening, or require hospitalization may be considered serious when, based upon

appropriate medical judgment, they may jeopardize the patient or subject and may require medical or surgical intervention to prevent one of the outcomes listed in this definition.

8.3.3 CLASSIFICATION OF AN ADVERSE EVENT

8.3.3.1 SEVERITY OF EVENT

For AEs not included in the protocol defined grading system, the following guidelines will be used to describe severity.

1. **Mild** – Events require minimal or no treatment and do not interfere with the participant's daily activities.
2. **Moderate** – Events result in a low level of inconvenience or concern with the therapeutic measures. Moderate events may cause some interference with functioning.
3. **Severe** – Events interrupt a participant's usual daily activity and may require systemic drug therapy or other treatment. Severe events are usually potentially life-threatening or incapacitating. Of note, the term "severe" does not necessarily equate to "serious".

8.3.3.2 RELATIONSHIP TO STUDY INTERVENTION/EXPERIMENTAL MANIPULATION

All AEs will have their relationship to study procedures, including the intervention, assessed by an appropriately-trained clinician based on temporal relationship and his/her clinical judgment. The degree of certainty about causality will be graded using the categories below.

- **Definitely Related** – There is clear evidence to suggest a causal relationship, and other possible contributing factors can be ruled out. The clinical event, including an abnormal laboratory test result, occurs in a plausible time relationship to study procedures administration and cannot be explained by concurrent disease or other drugs or chemicals. The response to withdrawal of the study procedures should be clinically plausible. The event must be pharmacologically or phenomenologically definitive.
- **Probably Related** – There is evidence to suggest a causal relationship, and the influence of other factors is unlikely. The clinical event, including an abnormal laboratory test result, occurs within a reasonable time after administration of the study procedures, is unlikely to be attributed to concurrent disease or other drugs or chemicals, and follows a clinically reasonable response on withdrawal.
- **Potentially Related** – There is some evidence to suggest a causal relationship (e.g., the event occurred within a reasonable time after administration of study procedures). However, other factors may have contributed to the event (e.g., the participant's clinical condition, other concomitant events). Although an AE may rate only as "possibly related" soon after discovery, it can be flagged as requiring more information and later be upgraded to "probably related" or "definitely related", as appropriate.
- **Unlikely to be related** – A clinical event, including an abnormal laboratory test result, whose temporal relationship to study procedures administration makes a causal relationship improbable (e.g., the event did not occur within a reasonable time after administration of the study procedures) and in which other drugs or chemicals or underlying disease provides plausible explanations (e.g., the participant's clinical condition, other concomitant treatments).

- **Not Related** – The AE is completely independent of study procedures administration, and/or evidence exists that the event is definitely related to another etiology. There must be an alternative, definitive etiology documented by the clinician.

8.3.3.3 EXPECTEDNESS

A clinician with expertise in MG will be responsible for determining whether an AE is expected or unexpected. An AE will be considered unexpected if the nature, severity, or frequency of the event is not consistent with the risk information previously described for the study procedures.

8.3.4 TIME PERIOD AND FREQUENCY FOR EVENT ASSESSMENT AND FOLLOW-UP

The occurrence of an AE or SAE may come to the attention of study personnel during study visits and interviews of a study participant.

All AEs, not otherwise precluded per the protocol, will be captured on the appropriate eCRF. Information to be collected includes event description, time of onset, clinician's assessment of severity, relationship to study procedures (assessed only by those with the training and authority to make a diagnosis), and time of resolution/stabilization of the event. All AEs occurring while on study will be documented appropriately regardless of relationship. All AEs will be followed to adequate resolution.

Any medical or psychiatric condition that is present at the time that the participant is screened will be considered as baseline and not reported as an AE. However, if the study participant's condition deteriorates at any time during the study, it will be recorded as an AE.

Changes in the severity of an AE will be documented to allow an assessment of the duration of the event at each level of severity to be performed. Documentation of onset and duration of each episode will be maintained for AEs characterized as intermittent.

Study staff will record events with start dates occurring any time after the first acupuncture treatment session until the last post-treatment visit for each group. After the first acupuncture study and until study completion, study staff will inquire about the occurrence of AE/SAEs. All reported events will be monitored until the last post-treatment visit for each group. We will also conduct a 2-week follow up phone call for Group 2 to collect information on any adverse events. Any reported event that is definitely or probably related to the intervention will be followed until resolution or stabilization.

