- Duration: Approximately 20 minutes via phone
- Research staff will:
 - Complete the Medication Review short form in the relevant electronic case report forms (eCRFs) in Research Electronic Data Capture (REDCap), a secure web-based system.
 - Interview patients using the MG-QOL15 and MG ADL surveys and document in REDCap.

4. Study Intervention (Groups 1 & 2)

- Duration: Each visit approximately 1 hour
- A study acupuncturist will:
 - Complete the Adverse Events (AE) Reporting, Medication Review, and Treatment Adherence in the relevant eCRFs in REDCap.
 - Perform the acupuncture treatment.

5. Post-treatment Visit 1 (Groups 1 & 2)

- Duration: Approximately 20 minutes via phone
- Research staff will:
 - Complete the AE Reporting and Medication Review forms in the relevant eCRFs in REDCap.
 - Interview patients using the Symptom Severity Scale (from the treatment log), MG-QOL15, and MG ADL surveys and document in REDCap.
 - Ask qualitative survey questions about the participant's experience with acupuncture.

6. Post-treatment Visit 2 (Group 1 only)

- Duration: Approximately 20 minutes via phone
- Research staff will:

- Complete the AE Reporting and Medication Review forms in the relevant eCRFs in REDCap.
- Interview patients using the Symptom Severity Scale (from the treatment log), MG-QOL15, and MG ADL surveys and document in REDCap.
- Ask qualitative survey questions about the participant's experience with acupuncture.

7. 2-week follow up call (Group 2 only)

- Duration: Approximately 5 minutes via phone
- Research staff will:
 - Complete the AE Reporting in the relevant eCRFs in REDCap.

8. Early Withdrawal Call (for individuals who withdraw from the study early)

- Duration: Approximately 20 minutes via phone
- Research staff will:
 - Complete the AE Reporting and Medication Review forms in the relevant eCRFs in REDCap.
 - Interview patients using the Symptom Severity Scale (from the treatment log), MG-QOL15, and MG ADL surveys and document in REDCap. Ask qualitative survey questions about the participant's experience with acupuncture.

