4.4 END-OF-STUDY DEFINITION

A participant is considered to have completed the study if he or she has completed study treatment visits and assessments. The end of the study is defined as completion of the last post-treatment visit for each group.

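### Section 8.3.4 gives two incompatible rules for how long adverse events are followed, and its recording window for Group 2 closes before the safety call scheduled to collect events.

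*Combined protocol and SAP*

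**What the plan says.** On duration of follow-up, Section 8.3.4 of the combined protocol and SAP first says "All AEs will be followed to adequate resolution". Its last paragraph says "All reported events will be monitored until the last post-treatment visit for each group" and ends with "Any reported event that is definitely or probably related to the intervention will be followed until resolution or stabilization".

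On which events are recorded, that last paragraph opens with "Study staff will record events with start dates occurring any time after the first acupuncture treatment session until the last post-treatment visit for each group" and continues "After the first acupuncture study and until study completion, study staff will inquire about the occurrence of AE/SAEs". It then adds "We will also conduct a 2-week follow up phone call for Group 2 to collect information on any adverse events".

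Section 4.4 states "The end of the study is defined as completion of the last post-treatment visit for each group". In Section 1.3 the second post-treatment visit is for Group 1 only, so Group 2's only post-treatment visit is Visit 27. The 2-week call is a separate contact numbered Visit 28. The visit description there gives the call one task, completing the adverse event form.

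**The concern.** Two practical questions have no single answer in the text.

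The first is what staff should do with an event that is still open at the last post-treatment visit and is not graded definitely or probably related. One sentence keeps following it; the later text lets it go. The Potentially Related category matters most here, because Section 8.3.3.2 allows such an event to be flagged for more information and upgraded later. If follow-up stops at the visit, that information may never arrive. Section 8.3.4 also asks for the time of resolution or stabilization, which could stay blank for such events.

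The second is whether an event that a Group 2 participant first reports at Visit 28, with onset after Visit 27, belongs in the data. The call exists to ask about it, but the start-date rule does not admit it.

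The plan has little else to fall back on for safety. Section 9.4.4 reports adverse events as Section 8.3 describes and plans no other formal safety analysis, and Section 10.1.6 states that there is no Data Safety Monitoring Board.

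**Working it through.** There is no stated figure to reproduce. The check sets the sentences against each other and against the schedule.

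**Step 1: follow-up rules by causality category.** Section 8.3.3.2 has five categories. Rule A is the sentence covering all AEs. Rule B is the later pair of sentences read together: every reported event to the last post-treatment visit, and definitely or probably related events to resolution or stabilization.

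| Category | Rule A: followed past the last visit if unresolved | Rule B: followed past the last visit if unresolved |
|---|---|---|
| Definitely Related | yes | yes |
| Probably Related | yes | yes |
| Potentially Related | yes | no |
| Unlikely to be related | yes | no |
| Not Related | yes | no |

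Rule A covers 5 categories and Rule B covers 2, so the rules disagree on 5 − 2 = 3. Treating Rule A as the general statement does not remove the conflict, because the relatedness limit in Rule B would then do nothing.

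**Step 2: Group 2's recording window against its visits.** From Section 1.3:

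- Treatment: Visits 3 to 26. The window opens after the first session.
- Post-treatment Visit 1: Visit 27. This is Group 2's last post-treatment visit, so the start-date window closes here, and so does the study under Section 4.4.
- 2-week call: Visit 28. The adverse event form is completed here.

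The literal window therefore closes one scheduled contact before the call.

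**Step 3: does another sentence extend the window?** The sentence on inquiry runs to study completion. Section 4.4 ends the study at the last post-treatment visit, which for Group 2 is again Visit 27. Section 4.4 also defines a participant's own completion by treatment visits and assessments. That could be stretched to include the call, but the text does not say so.

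**Step 4: length of the gap.** For Group 1, Section 9.4.2 places the second post-treatment assessment 12 weeks after treatment, so its recording window runs about that long beyond the last session. For Group 2 the length cannot be computed. The documents do not give the interval from last treatment to Visit 27, or say whether the two weeks of the call run from the last treatment or from Visit 27.

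**The case against.** The strongest reply is that the intent is clear. The sentence on the Group 2 call is worded as an addition to what precedes it, the schedule marks the call for adverse event reporting, and staff are told to complete the form. Anyone following the schedule would record these events. Serious events and unanticipated problems go to the IRB within 10 working days of the team learning of them (Sections 8.3.5, 8.3.6 and 8.4.2), whatever the start-date window says. No between-group comparison of adverse events is planned, so no formal test is distorted.

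Most of this stands, and it rules out two stronger readings.

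- A reader might infer that Group 2 has no recordable period after treatment and that its adverse events will be understated. That would require staff to complete the form and then set its content aside, which no section directs. It is a risk under the literal wording, not a demonstrated loss.
- A reader might infer that three follow-up sentences all disagree. The second and third fit together as an ordinary two-tier rule. The contradiction is between the all-AEs sentence and that pair.

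It is also fair to say that a safety call after the defined end of study does not by itself make Section 4.4 wrong. Section 4.4 matters here only because the inquiry period is tied to study completion.

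The reply leaves two things unanswered. Intent does not change the start-date rule, under which an analyst could properly exclude a late Group 2 event. And nothing in the documents reconciles the all-AEs sentence with the two-tier text.

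**Conclusion.** Section 8.3.4 contains two internal conflicts, and both are minor. The follow-up conflict affects events unresolved at the last post-treatment visit in three of the five causality categories. The recording conflict affects Group 2 events that start between Visits 27 and 28, on the literal reading of the start-date rule. The documents give no basis for estimating how many events either would involve.

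The consequence is limited to safety data: whether some late events are counted and whether some open events get a recorded outcome. The MG-QOL15 comparison, the randomization and the sample size do not depend on it. The conclusion rests on the current wording of Sections 1.3, 4.4, 8.3.3.2 and 8.3.4, and takes Visit 27 as Group 2's last post-treatment visit, as the schedule shows.

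**What to change.** Reconcile the follow-up sentences in Section 8.3.4 into one consistent rule. Whether that rule distinguishes events by relatedness, and where follow-up ends, is for the investigators to decide.

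Extend the start-date window for Group 2 through the Visit 28 call, so that events collected there are recorded and reported. State what the two weeks are counted from. Check Section 4.4 and the inquiry sentence for consistency with that window.

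The cost is about one paragraph of protocol wording. The call is already scheduled and its adverse event form already specified, so the recording change adds no visit. Any extra follow-up work depends on the rule the investigators choose.

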7.1 DISCONTINUATION OF STUDY INTERVENTION/EXPERIMENTAL MANIPULATION

When a participant who signed the consent form chooses to discontinue participation in the study or study intervention, or if the principal investigator and co-investigators determine that a participant should discontinue participation, they will be withdrawn from the study. A withdrawal will either be defined as 'Patient Withdrawal' or 'Principal Investigator Withdrawal'. The participant will be asked to complete an early withdrawal phone call 7-14 days from the date the intervention was discontinued. The purpose of the phone call will be to record any AEs or serious adverse events (SAEs) that may have occurred after the discontinuation of treatment. Research staff will attempt to call the participant up to 3 times.

The data that will be collected at the time of study withdrawal will include the following:

- The reason(s) for discontinuation of the study intervention

The data that will be collected during the early withdrawal phone call will include the following:

- AEs or SAEs that occurred since the time of withdrawal

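### Adverse events are not solicited during Group 2's 12 untreated control weeks, and section 8.3.4 is inconsistent about whether events in that time are to be recorded

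*Combined protocol and SAP*

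**What the plan says.** Section 8.3.4 opens AE collection at the start of acupuncture, in two sentences. On recording: "Study staff will record events with start dates occurring any time after the first acupuncture treatment session", with the window closing at each group's final post-treatment visit. On asking: "After the first acupuncture study and until study completion, study staff will inquire about the occurrence of AE/SAEs".

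The schedule in section 1.3 agrees. Its AE row is blank in both pre-treatment columns and is marked from the Study Intervention column onward. The narrative for Pre-treatment Visit 2, the Group 2 call before its treatment begins, starts with "Complete the Medication Review short form in the relevant electronic case report forms" and then lists MG-QOL15 and MG ADL. It names no AE form. At Post-treatment Visit 1, by contrast, staff are told: "Complete the AE Reporting and Medication Review forms in the relevant eCRFs in REDCap".

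The same section 8.3.4 also contains two broader statements. One is "All AEs occurring while on study will be documented appropriately regardless of relationship". The other is that if a participant's "condition deteriorates at any time during the study, it will be recorded as an AE". Section 8.3.1 defines an AE as "any untoward medical occurrence associated with the use of an intervention in humans". Section 9.4.4 classifies events by severity, relatedness and expectedness, and plans no further formal safety analysis.

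**The concern.** The synopsis makes Group 2 the control for the first 12 weeks, so the trial has a randomised, concurrent, untreated arm. The AE plan does not use it. Followed as scheduled, solicited AEs come only from treated and post-treatment time.

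This matters because section 2.2.1 lists worsening of the symptoms being treated as an uncommon side effect of acupuncture, and here those symptoms are MG itself. Section 8.3.3.2 asks a clinician to judge relatedness partly on whether underlying disease explains the event. A reader who sees hospitalisations or MG worsenings reported during acupuncture would want to know how many such events arose over the same weeks without it.

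The wording also leaves room for two practices. One staff member could apply the start-date sentence and record nothing from the wait. Another could apply the broader sentences and record whatever a participant mentions. The count from the control weeks would then depend on who took the call.

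**Working it through.** The plan states no figure for AE ascertainment, so there is none to reproduce. The check is a count from the schedule, then a look at how much the missing data could tell us.

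**Inputs.** 10 per group (sections 4.1 and 9.2); enrolment target 25 at 1:1 (sections 1.1, 6.3 and 9.2); 12-week delay, 12-week treatment and 24 sessions (sections 1.1 and 6.1.2); a 2-week call for Group 2 and visit numbers (section 1.3). Nominal visit timing and no dropout are assumed. For Group 1, the after-treatment period is the 12 weeks to Post-treatment Visit 2 (section 9.4.2).

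**Person-weeks covered by a scheduled AE inquiry, 10 per group**

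| Period | Group 1 | Group 2 |
|---|---|---|
| Untreated control | none exists | 0 of 10 × 12 = 120 |
| On treatment | 10 × 12 = 120 | 10 × 12 = 120 |
| After treatment | 10 × 12 = 120 | 10 × 2 = 20 |

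- Share of the randomised weeks 0–12: 120 / (120 + 120) = 50% has no inquiry.
- Share of Group 2's time on study: 12 / (12 + 12 + 2) = 12/26 = 46%.
- With 25 randomised and 12 or 13 in Group 2: 12 × 12 = 144 or 13 × 12 = 156 person-weeks.

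**Scheduled inquiries per person in weeks 0–12.** Group 1: Visits 2–25 (24) plus Visit 26 (1) = 25. Group 2: 0.

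**What the control data could show.**

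- Zero events in 10 people: exact 95% upper limit = 1 − 0.025^(1/10) = 30.8%. In 13 people: 1 − 0.025^(1/13) = 24.7%.
- 3/10 against 1/10: difference 20 points, Newcombe 95% CI −16.0 to +51.4.

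**Illustration only.** The documents give no background event rate. Let r be the assumed 12-week risk of a recordable event in an untreated person. With 10 in Group 2, expected participants with an event = 10r and the chance of at least one = 1 − (1 − r)^10.

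| r | Expected | Chance of at least one |
|---|---|---|
| 0.05 | 0.5 | 40.1% |
| 0.10 | 1 | 65.1% |
| 0.20 | 2 | 89.3% |

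**Reading the sentences together.** If the start-date sentence governs, helped by the intervention wording in 8.3.1 and by the carve-out in 8.3.4 for AEs the protocol excludes, the control weeks fall outside the window. If the broader sentences govern, events from those weeks are recordable but unsolicited. Neither reading puts an AE question to Group 2 before treatment.

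**The case against.** The strongest reply is that this is a deliberate scope. The start date, the schedule and the visit narrative agree with one another. Section 3 has no safety objective. Section 9.4.4 only classifies events, and under sections 8.3.3.2 and 8.3.3.3 relatedness rests on clinical judgement and expectedness on stated risk information. No planned result uses a concurrent control rate, so none is invalidated. That stands, and it limits how much weight the point can carry. It does not explain why 8.3.4 also promises to document everything that happens on study.

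A reader might go further and infer that nothing from the control weeks can be recorded. The documents do not support that. The two broader sentences in 8.3.4 let volunteered events and MG deterioration be entered. Sections 8.3.5 and 8.3.6 require serious events to be evaluated and reported once the investigator learns of them, with no condition that acupuncture has started. The Early Withdrawal Call in section 1.3 includes the AE form, although section 7.1 describes its content as "AEs or SAEs that occurred since the time of withdrawal". What remains true is that nobody is scheduled to ask those who complete the wait.

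A reader might also infer that MG worsening in untreated patients goes unmeasured. It does not: Pre-treatment Visit 2 collects MG-QOL15, MG ADL and a medication review, and both scales are compared between arms.

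Finally, adding a question at week 12 would not make the arms like for like. Group 1 will have been asked at 24 sessions, Group 2 once by recall, and everyone is unblinded. This objection is right, and it rules out treating the weeks 0–12 counts as a formal comparison.

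**Conclusion.** The concern holds in a limited form. AEs are not solicited in Group 2's untreated control weeks, and section 8.3.4 is inconsistent on whether events there are to be recorded. The loss is a solicited count of discrete events that could serve as a descriptive untreated background: 0 of 120 control person-weeks at 10 per group, or 0 of 144–156 with 25 randomised. Group 1's weeks after treatment are asked about but are no substitute, because those participants have already been treated and carryover is possible.

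No primary or secondary efficacy analysis is affected, and the intervals above show that the missing data could not support a test. The gap is still worth closing, because the instructions conflict and the remedy is cheap.

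This rests on reading the first session as each participant's own, which the schedule supports, and on nominal timing without dropout. The expected event numbers rest on assumed risks of 5–20% and only illustrate the scale.

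**What to change.** - **Section 8.3.4:** replace the start-date and inquiry sentences with a rule that AEs are recorded and asked about from randomisation to last study contact in both groups, whether or not acupuncture has started. State that 8.3.1 is to be read accordingly, so that its reference to use of an intervention does not exclude the wait.
- **Section 1.3:** add the existing AE form to Pre-treatment Visit 2, in both the schedule and the narrative.
- **Section 9.4.4:** tabulate AEs descriptively by period (control, on treatment, after treatment) with participants affected and person-weeks. Keep all of Group 1's session-level data. State that ascertainment was unblinded and more frequent in Group 1 (24 sessions plus one call, against one recall call), so weeks 0–12 counts are not a formal comparison. The exclusion of other formal safety analyses can stay.
- **Participants already past week 12:** state that control-period AEs were not elicited, so that silence is not read as zero events.

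The cost is a protocol amendment, one existing form added to an existing 20-minute call, and one descriptive table. No visits are added. The downsides are that 12-week recall misses mild events, asking frequency stays unequal between groups, and the numbers remain too small for a test.
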